Appendix 3: Contraceptive Guidance and Collection of Pregnancy Information

Definitions:

Woman of Childbearing Potential (WOCBP)

A woman is considered fertile following menarche and until becoming postmenopausal unless permanently sterile (see below).

If fertility is unclear (e.g., amenorrhea in adolescents or athletes) and a menstrual cycle cannot be confirmed before first dose of study treatment, additional evaluation should be considered.

Women in the following categories are not considered WOCBP:

1. Premenarchal.
2. Premenopausal female participant with 1 of the following:
 - Documented hysterectomy.
 - Documented bilateral salpingectomy.
 - Documented bilateral oophorectomy.
3. Postmenopausal female:
 - A postmenopausal state is defined as no menses for 12 months without an alternative medical cause. A high FSH level in the postmenopausal range may be used to confirm a postmenopausal state in women not using hormonal contraception or HRT. However, in the absence of 12 months of amenorrhea, confirmation with more than one FSH measurement.
 - Females on HRT and whose menopausal status is in doubt will not be included.

Contraceptive guidance:

The contraceptive measures to be used by the participants in this study are described in the inclusion criteria (see Section [6.1](#)).

Collection of pregnancy information:

The collection of pregnancy information is described in Section [9.4.5](#).

Appendix 4: Vital Signs and Electrocardiogram (ECG) normal ranges

Normal ranges applicable for vital signs:

Parameter	Normal ranges
Systolic Blood Pressure	[90-140] mmHg
Diastolic Blood Pressure	[50-90] mmHg
Pulse Rate	[45-100] beats/min
Orthostatic hypotension: decrease in systolic BP > 20 mmHg or diastolic BP > 10 mmHg when changing from the supine to the standing position.	
Note: Clinical signs and symptoms of postural hypotension (dizziness, syncope, etc.,) should be also evaluated, regardless of vital signs.	
Body temperature	[35.0-37.5] °C

Normal ranges applicable for ECG:

Parameter	Normal ranges
QRS Duration, Aggregate	≤110 msec
PR Interval, Aggregate	≤220 msec
ECG Mean Heart Rate	[45-100] beats/min
QTcF Interval, Aggregate	≤450 msec (males) ≤470 msec (females)

Appendix 5: Time windows for performing safety and pharmacokinetic (PK) assessments

Procedure	Time Point	Time Window
Safety laboratory assessments (hematology, clinical chemistry, coagulation, urinalysis)	Inferior or equal to H2	± 15 min
]H2-H6]	± 30 min
]H6-H24]	± 60 min
	Superior to H24	± 120 min
12-lead ECG	[5-10[min	± 2 min
	[10-15] min	± 5 min
]15-30] min	± 10 min
]30 min-H2]	± 15 min
]H2-H6]	±30 min
]H6-H24]	± 60 min
	Superior to H24	± 120 min
PK blood collection	[H0.5-H0.75]	±1 min
	[H1-H1.5]	±3 min
	[H2-H12]	±5 min
	H24	± 15 min
	H36	± 30 min
	[H48-H72]	± 120 min
Vital Signs	Inferior or equal to H2	± 15 min
]H2-H6]	± 30 min
]H6-H24]	± 60 min
	Superior to H24	± 120 min

11.3.7. Pregnancy test	26
12. Procedures and data formats	26
13. Reporting conventions.....	26
14. References.....	27
15. Appendices.....	28
15.1. Appendix 1 - Schedule of activities of the study.....	28
15.2. Appendix 2 - Criteria for Potentially Clinically Significant Abnormalities (PCSA)	32

LIST OF ABBREVIATIONS AND DEFINITION OF TERMS

ABBREVIATION	DEFINITION
ADPP	ADaM Pharmacokinetic Parameters dataset
AE	Adverse Event
ALP	ALkaline Phosphatase
ALT	ALanine aminoTransferase
AST	ASpartate Aminotransferase
ATC	Anatomic Therapeutic Chemical
AUC	Area Under the Curve
AUC_%Extrap_obs	Residual area expressed in percentage
AUC _{last}	Area Under the Curve from time zero to last quantifiable plasma concentration
AUC _{inf}	Area Under the Curve from time zero to infinity
BLQ	Below the Limit of Quantification
BMI	Body Mass Index
CI	Confidence Interval
CK	Creatine Kinase
CL/F	Apparent total body clearance
C _{last}	Last observed quantifiable plasma concentration
C _{max}	Maximum observed plasma concentration
COVID-19	Coronavirus disease 2019
CRF	Case Report Form
CSR	Clinical Study Report
CV	Coefficient of Variation
eCRF	electronic Case Report Form
ECG	ElectroCardioGram
EMA	European Medicines Agency
EOS	End Of Study
FDA	Food and Drug Administration
FSH	Follicle Stimulating Hormone
GGT	Gamma Glutamyl Transferase
GMR	Geometric Mean Ratio
HBsAg	Hepatitis B surface Antigen
hCG	human Chorionic Gonadotropin

ABBREVIATION	DEFINITION
HGB	Hemoglobin
HIV	Human Immunodeficiency Virus
i.e.	id est
ICH	International Conference on Harmonisation
IMP	Investigational Medicinal Product (synonymous with “study drug”)
λ_z	First order terminal elimination rate constant
LLN	Lower Limit of Normal range
MedDRA	Medical Dictionary for Regulatory Activities
MR	Metabolic Ratio
MRT	Mean Residence Time
MW	Molecular Weight
NA	Not Applicable
NC	Not Calculated
NCI-CTCAE	National Cancer Institute - Common Terminology Criteria for Adverse Events
ND	Not Determined
PCR	Polymerase Chain Reaction
PCSA	Potentially Clinically Significant Abnormalities
PK	Pharmacokinetics
PT	Preferred Term
QRS	QRS interval duration
QT	Time interval for ventricular depolarisation and repolarisation
QTc	Corrected QT interval
QTcF	QT interval corrected using Fridericia's formula
SAE	Serious Adverse Event
SAP	Statistical Analysis Plan
SAS®	Statistical Analysis System®
SD	Standard Deviation
SEM	Standard Error of the Mean
SOC	System Organ Class
SOP	Standard Operating Procedure
$t_{1/2}$	Terminal elimination half-life
T _{last}	Time to reach last observed quantifiable plasma concentration
T _{max}	Time to reach maximum observed plasma concentration

ABBREVIATION	DEFINITION
TEAE	Treatment-Emergent Adverse Event
TOST	Two One-Sided Test
ULN	Upper Limit of Normal range
ULQ	Upper Limit of Quantification
Vz/F	Apparent volume of distribution
WHO	World Health Organisation

1. Introduction

The Statistical Analysis Plan (SAP) details the statistical methodology to be used in analysing study data and outlines the statistical programming specifications, tables, figures and listings. It describes the safety and pharmacokinetics (PK) variables and analysis sets, anticipated data transformations and manipulations, and other details of the analyses not provided in the study protocol.

The analyses described are based upon the final clinical study protocol V1.2 dated 22 June 2022 and will be prepared in accordance with the International Conference on Harmonisation (ICH) E9.

The statistical analyses will be performed by the Biostatistics unit of BIOTRIAL BIOMETRICS in agreement with the sponsor.

The SAP will be validated and signed before the first visit of the first participant.

2. Study objectives

2.1. Primary objective

The primary objective is to demonstrate the bioequivalence of binimatinib 1 x 45 mg tablet Test formulation in comparison to 3 x 15 mg tablet Reference formulation in healthy participants under fasted conditions.

2.2. Secondary objectives

The secondary objectives are:

- to measure secondary PK parameters of binimatinib and PK parameters of the metabolite (AR00426032)
- to evaluate the safety and tolerability of binimatinib as a 1 x 45 mg Test tablet in comparison to 3 x 15 mg Reference tablets in healthy participants.

3. Study methodology

3.1. Protocol overview

This will be a randomized, single-center, open-label, two-sequence, two-period, crossover phase I study to demonstrate the bioequivalence of binimatinib 3 x 15 mg and 1 x 45 mg tablets in healthy participants. The Reference (R) formulation will be the currently commercially available tablet containing 15 mg of binimatinib as active substance, administered as three tablets for a total of 45 mg binimatinib. The Test (T) formulation will be the tablet containing 45 mg of binimatinib as active substance in one tablet.

Participants will be randomized to one of 2 treatment sequences (RT or TR) containing 2 treatment periods, with at least a 7-day washout between each dose.

The study will consist of:

- a screening period between 21 and 2 days before the first study treatment administration on Period (P) 1 Day (D) 1,
- 2 treatment periods of 5 days each (including one ambulatory visit at D4 per period),
- a washout of at least 7 days between P1D1 and P2D1,

- an End of Study (EOS) visit to be performed 30 (\pm 3) days after the last study treatment administration or discontinuation.

Study treatments will be given by the oral route in fasted condition.

In each treatment period, following the 48h post-dose procedures, the participants will be discharged and will return for an ambulatory visit on D4, and then return for the next treatment period or an EOS visit.

The schedule of activities is available in section 15.1.

3.2. Planned analyses

Final analyses will be performed when all participants complete the study and after the database lock.

4. Sample Size

The primary objective of this study is to demonstrate bioequivalence between the Test 1 x 45 mg binimetinib tablet and the Reference 3 x 15 mg binimetinib commercial tablets, based on PK endpoints C_{max} , AUC_{inf} and AUC_{last} .

The null hypothesis is that the true ratio of the geometric mean of the Test treatment to the geometric mean of the Reference treatment, $\mu(T)/\mu(R)$, for the C_{max} , AUC_{inf} and AUC_{last} is either <0.80 or >1.25 . The alternate hypothesis is that the true ratio of the geometric mean of the Test treatment to the geometric mean of the Reference treatment for the C_{max} , AUC_{inf} and AUC_{last} , is ≥ 0.80 and ≤ 1.25 . For each PK parameter designated as a primary endpoint, a two one-sided t-test (TOST) [1] procedure with $\alpha=0.05$ for each one-sided test will be used to test this set of hypotheses.

Bioequivalence will be declared if the 90% confidence interval (CI) for the true ratio of test to reference geometric means falls entirely within the range of 0.80 to 1.25 for all primary parameters (i.e the null hypothesis must be rejected), in accordance with the European Medicines Agency (EMA) and Food and Drug Administration (FDA) guidelines on the investigation of bioequivalence [2][3].

Based on these criteria, assuming intra participant coefficient of variation (CV_{intra}) of C_{max} to be around 25% as observed on the pilot study [4] and a “Test/Reference” mean ratio of 1.05; thirty-six participants are needed to achieve a power of 90% at an alpha of 0.05.

Up to 40 participants will be included into the study to complete the study with at least 36 evaluable participants.

5. Changes to the planned analysis from protocol

Not applicable.

6. Statistical considerations

Demography and safety data will be analysed using SAS[®] software version 9.4 or higher (SAS institute Inc. Cary NC USA).

Pharmacokinetic (PK) data will be analysed using Phoenix[®] WinNonlin[®] version 8.1 or higher (Certara USA, Inc., Princeton, NJ) and SAS[®] software version 9.4 or higher (SAS Institute Inc. Cary NC USA).

Descriptive statistics will be supplied according to the nature of the criteria:

- Quantitative variable: number of participants, arithmetic mean, standard deviation (SD), standard error of the mean (SEM), minimum, median and maximum, and quartiles if necessary [with geometric mean, arithmetic and geometric CV, and quartiles for PK analyses].
- Qualitative variable: number of participants, absolute and relative frequencies per class.
- Percentages will be provided with one decimal place.

Unless specified otherwise, the calculation of percentages will be based on the number of observed values. Therefore, counts of missing values will be included in the denominator and displayed as a separate category if any.

For the values measured outside of the treatment periods, data will be organised overall and, for description at baseline, by sequence:

- Test/Reference
- Reference/Test

With the following footnote: " Reference: binimetinib 3 x 15 mg tablet; Test: binimetinib 1 x 45 mg tablet.".

For the values obtained during the treatment periods, data will be organised by formulation group:

- binimetinib 1 x 45 mg tablet,
- binimetinib 3 x 15 mg tablet.

All safety listings will be sorted by participant, sequence and measurement time if applicable.

All pharmacokinetics listings will be sorted by treatment group, participant and measurement time.

All listings containing an evaluation date will display the study day defined as the day relative to the first administration of study drug:

- If evaluation precedes first drug administration then:
(date of evaluation) - (date of first study drug administration)
- Study day -1 will be defined as the day prior to the first administration date.
 - If evaluation is on or after the first drug administration then:
(date of evaluation) – (date of first study drug administration) + 1
- Study day 1 will be defined as the day of the first administration date.
- There will be no study day 0.

Handling of missing, retest values and unscheduled visits

No management of missing values or values below/above a limit of detection/quantification will be performed, except for pharmacokinetic values (see section 9.1). In clinical laboratory data, “<LOQ” or “>ULQ” is reported in the qualitative variable. When converting the qualitative variable to the quantitative variable, “<LOQ” or “>ULQ” will be automatically treated as missing.

For all parameters and for participants with retest values, the last non-missing value will be used for the measurement time before the first IMP administration within each period (provided it was measured before IMP administration within each period) and the first non-missing value will be used for the measurement time after the first IMP administration within each period.

Unscheduled visits will not be analysed but presented in listings only.

Handling of incomplete dates

No management of incomplete dates will be performed. The incomplete dates will be labelled as such in the listings.

Baseline definition

For all parameters, baseline will be defined as the last available assessment prior to the first IMP administration within each period, including additional assessments (where applicable). Assessments that occurred on the same day as first dose, when time of assessment is not available, will be assumed to be prior to first dose.

Duration

Duration (in days, hh:mm) will be calculated by the difference between the start and stop date and time (e.g. duration of AE (days, hh:mm) = end of AE date and time - AE onset date and time).

Duration (in days) will be calculated by the difference between the start and stop date + 1 (e.g. duration of a medication (days) = end of medication date - onset of medication date + 1).

Type I error rate

Unless stated otherwise, statistical tests will be two-sided and will be carried out at the 5% level of significance.

7. *Description of study participants*

7.1. *Definition of analysis sets*

The following analysis sets will be defined:

Enrolled set: all participants who signed the ICF for the study.

Screened set: all enrolled participants having successfully completed the screening period.

Randomized set: all randomized participants.

Safety set: all included participants having taken at least one dose of study treatment, including those who did not complete the study.

Pharmacokinetic set: all of the participants who have taken one dose of study treatment in the two periods without any event (including no vomiting within 4 hours after dosing) and/or important protocol deviation affecting PK evaluation, with complete PK profiles in these two periods, i.e. sufficient PK concentration data to support the calculation of primary PK criteria (see section 9.1).

The analysis sets will be precisely defined and validated during the data review meeting and prior to database lock..

The safety and pharmacokinetic sets will be analysed using participants as treated. The randomized set will be analysed using participants as randomized.

7.2. *Participant disposition*

A summary table with the description of the number of screened participants, the number of randomized participants, the number of participants who completed the study and the number

of participants who discontinued the study, classified by main reason of withdrawal, will be prepared by sequence and overall for the participants in the screened set. Corresponding individual listings will be provided.

A summary table with the description of the number and percentage of participants in each analysis set (Randomized set, Safety set and Pharmacokinetic Set) will be prepared by sequence and overall. A specific listing of participants excluded from safety and/or pharmacokinetic analyses will be provided with the reason(s) for exclusion.

A summary table with the number and percentage of participants at each period will be prepared by treatment group and overall on the participants in the randomized set.

Listings with end of study status and study visit dates will also be generated.

In addition, due to possible impact of COVID-19 pandemic on participants' disposition, the following disposition table will be presented for all randomized patients by sequence:

- number (%) of participants infected (i.e. at least one AE related to COVID-19 and/or positive Polymerase Chain Reaction test result).
- number (%) of discontinued participants due to COVID-19 and reasons of discontinuation,
- number (%) of participants impacted (with at least one important protocol deviation due to COVID-19 or for whom the conduct of the study has been impacted (missed visit, remote visit, unscheduled visit, etc.)),
- number (%) of participants with important protocol deviations due to COVID-19.

7.3. *Protocol deviations*

A summary table by sequence and overall with the number and percentage of participants presenting all protocol deviations judged important during the data review meeting will be prepared for the participants in the randomized set. All important protocol deviations will be listed and important protocol deviations due to COVID-19 will be flagged if applicable.

8. *Demographic data and baseline characteristics*

The analyses of the demographic and baseline characteristics will be performed on the randomized set.

8.1. *Demographic data*

The participants' demographic characteristics will be summarised by sequence and overall, and listed:

- age at screening (years) – continuous,
- sex,
- ethnicity,
- height at screening (cm)
- weight at screening (kg)
- Body Mass Index (BMI) recorded at screening (kg/m²)

8.2. *Other baseline characteristics*

All parameters recorded before dosing (COVID-19 vaccination status, smoking and alcohol history) will be summarised by sequence and overall, and listed.

Positive results as well as all individual data for urine drug screen (benzodiazepines, cocaine, cannabinoids, morphine, amphetamines, methamphetamines and ecstasy), alcohol breath test and urine cotinine test performed at screening and on Day -1 of each period (see section 15.1) will be listed.

Positive results as well as all individual data for serology (Hepatitis B surface antigen, hepatitis C antibody and HIV) will be listed.

For postmenopausal female participants, serum follicle-stimulating hormone (FSH) and estradiol will only be listed.

8.3. Medical and surgical history and procedures

Information on medical and surgical history recorded at the screening visit and procedures will be coded according to the Medical Dictionary for Regulatory Activities (MedDRA) Version 24.0.

A table with the number and percentage of participants having at least one previous/ongoing medical history or one surgical history will be generated by sequence and overall, by System Organ Class (SOC) and Preferred Term (PT). Previous/ongoing medical history will be listed as well as prior surgeries and concomitant surgeries.

8.4. Prior and concomitant medications

Information on prior and concomitant medications will be coded according to the WHO Drug Dictionary version of March 2022 (B3 with primary ATC selection).

A prior medication will be defined as a medication stopped prior to the date and time of the first administration of IMP. Prior medications are recorded in the “Concomitant medication” eCRF page and identified by the “Taken prior to treatment start” variable.

A concomitant medication will be defined as a medication that is taken by participants any time during the treatment period (on or after the date and time of first IMP administration for each participant). If the date value does not allow allocation of a medication to the prior or concomitant category (missing or incomplete start or end date), this medication will be considered concomitant.

A table with the number and percentage of participants having taken at least one previous medication and a table with the number and percentage of participants having taken at least one concomitant medication will be generated by sequence and overall (overall and by medication class [2nd level of Anatomical Therapeutic Chemical (ATC)] and medication drug name). Prior and concomitant medications will be listed separately.

8.5. Compliance

A listing with IMP administration dates and times will be generated. Time of meals intake will also be listed.

9. Pharmacokinetic data

Plasma concentrations of binimetinib and corresponding non-compartmental derived PK parameters [AUC from time of administration to last observed plasma concentration (AUC_{last}), AUC_{inf}, C_{max}, T_{max} and AUC Test (T)/Reference (R) ratios] will be used as primary endpoints to evaluate the bioequivalence of binimetinib 1 x 45 mg tablet formulation in comparison to the commercialized 3 x 15 mg tablet formulation in healthy participants under fasted conditions.

The pharmacokinetic statistical analysis will be performed on the PK set.

9.1. Generalities

Reasons for exclusion:

Before concentration data are communicated by the bioanalytical laboratory, the following rules will lead to exclude a participant from the PK set:

- Any participant who discontinued with study treatment (no administration in the second period),
- Any participant having experienced vomiting or diarrhoea within 4 hours after dosing,
- Any participant having taken prohibited concomitant treatment or medication affecting PK throughout the study,
- Any participant for whom a washout of at least 7 days between each dose was not respected,
- Any participant who did not remain fasted for at least 10 hours before dosing,
- The following deviations will be discussed case by case:
 - Any deviation related to PK sample technical handling or storage,
 - Any participant with insufficient PK samples to support the calculation of primary PK criteria.

In the following cases (exceptions), the decision to exclude a participant from the statistical analysis (i.e. participant kept in the PK set but flagged and only listed, concentrations and parameters will not be used for statistical analysis) could be done after concentration data are communicated by the bioanalytical laboratory:

- 1) Any participant with lack of any measurable concentrations or only very low plasma concentrations for reference formulation (i.e. its AUC is less than 5% of reference formulation geometric mean AUC, calculated without inclusion of data from the outlying participant),
- 2) Any participant with non-zero baseline concentrations $> 5\%$ of C_{max} .

The following rules for **PK parameter calculation** after each administration will be used:

Actual sampling times will be used for deriving PK parameters.

- For plasma concentrations and PK parameters:
 - All BLQ values will be substituted according to the rules described in the following table and by type of analysis:

Substitution value if BLQ occurs:			
Type of analysis	Before T _{max}	After T _{max} & between 2 quantifiable concentrations	After T _{max} & NOT between 2 quantifiable concentrations
PK non-compartmental analysis	0	Missing	Missing
Descriptive statistics	0	0	0
Plotting of individual data	0	Missing	Missing
Listing of individual data	BLQ	BLQ	BLQ

- Some conditions for plasma PK parameters have to be fulfilled:
 - 1) the percentage of the extrapolated AUC (AUC_%Extrap_obs) should not exceed 20% of the AUC_{inf} of each individual profile,
 - 2) the elimination rate constant should be determined over a time interval equal to at least 2 x t_{1/2},
 - 3) the determination of λ_z should use only those data points judged to describe the terminal log-linear decline resulting in an adjusted coefficient of determination value R² (Rsq_{adj}) ≥ 0.8, and a minimum of 3 data points will be used in calculating λ_z excluding C_{max}.

If these conditions are not fulfilled, the following unreliable PK parameters will be flagged in the listings and will be excluded from the analysis:

- 1) if the time interval used for the determination of the elimination rate constant is inferior to 2 x t_{1/2} and/or not with a minimum of 3 data points and/or if the Rsq_{adj} < 0.8: λ_z, t_{1/2}, AUC_{inf}, CL/F, Vz/F, MRT and MR_{AUC}.
- 2) if AUC_%Extrap_obs > 20%: AUC_{inf}, CL/F, Vz/F, MRT and MR_{AUC}.

No graphic representation will be done if all values are BLQ.

The following rules for **mean plasma concentration calculation** will be used:

- If at least 3 of the values are evaluable (either BLQ values replaced by zero or numeric values): statistics will be calculated with the replaced and numeric values.
- If less than 3 values are evaluable: only the minimum and maximum will be presented and the other statistics will be considered as "Not Applicable" (NA).
- If at least one value is BLQ (replaced by 0), the geometric mean and its CV% will be presented as "Not Calculated" (NC).

For **summary statistics for PK parameters**:

- If at least 3 values are analysable and not missing: statistics will be calculated with the available values.

- If less than 3 values are analysable: only the minimum and maximum of the available numeric values will be presented. All other statistics will not be calculated and will be presented as "Not Determined" (ND).

All BLQ concentrations and missing data will be labelled as such in the concentration data listings.

9.2. *Plasma concentrations and pharmacokinetic parameters*

9.2.1. *Plasma parameters*

Blood samples will be drawn in each treatment period (see section 15.1) at pre-dose and at H0.5, H0.75, H1, H1.25, H1.5, H2, H3, H4, H5, H6, H8, H10, H12, H24, H36, H48 and H72 post-dose of each period.

Relevant plasma pharmacokinetic (PK) parameters of binimatinib and its metabolite AR00426032 will be calculated by standard non-compartmental methods for the participants with sufficient plasma concentration data (a PK profile with at least 3 quantifiable concentrations). The rules defined in the previous section (9.1) will be used.

The different areas under the concentration-time curve (AUC) will be calculated using the linear-log trapezoidal method: the linear trapezoidal method for increasing or equal concentrations and the logarithmic trapezoidal method for decreasing concentrations.

The following plasma pharmacokinetic parameters will be calculated for binimatinib and AR00426032:

Parameters (unit)	Definition
C_{max} (ng/mL)	Maximum observed plasma concentration
T_{max} (h)	Time to reach maximum observed plasma concentration
T_{last} (h)	Time to reach last observed quantifiable plasma concentration
AUC_{last} (ng/mL.h)	Area under the plasma concentration-time curve from time zero to the last quantifiable plasma concentration
AUC_{inf} (ng/mL.h)	Area under the plasma concentration-time curve from time zero to infinity, calculated as follows: $AUC_{inf} = AUC_{last} + \frac{C_{last}}{\lambda_z},$ where C_{last} is the last observed quantifiable concentration
λ_z (h)	First order terminal elimination rate constant
$t_{1/2}$ (h)	Terminal elimination half-life, calculated as follows: $t_{1/2} = \ln(2)/\lambda_z$
MRT (h)	Mean Residence Time, calculated as follows: $MRT = \frac{AUMC_{inf}}{AUC_{inf}}$ where $AUMC_{inf}$ is the area under the first moment curve from zero to infinity.

The following plasma pharmacokinetic parameters will be calculated only for binimatinib:

Parameters (unit)	Definition
$AUC_{-Extrap_obs}$ (%)	Residual area expressed in percentage

Parameters (unit)	Definition
CL/F (L/h)	Apparent total body clearance, calculated as follows: $CL/F = \text{Dose} / AUC_{inf}$
Vz/F (L)	Apparent volume of distribution, calculated as follows: $Vz/F = CL/F / \lambda_z$
MR _{AUC}	Metabolite-parent ratio based on AUC _{inf} accounting for differences in molecular weights (MW), calculated as follows: $MR_{AUC} = \frac{AUC_{inf\ AR00426032} / MW_{AR00426032}}{AUC_{inf\ binimetinib} / MW_{binimetinib}}$

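### SAP 9.2.1 withholds C_max and AUC_last from a Test profile with fewer than 3 quantifiable concentrations, so a near-complete Test failure would leave the bioequivalence model, although SAP 9.1 allows low-exposure removal for the Reference only

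*SAP*

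**What the plan says.** Four parts of the plan bear on a Test dose that delivers almost no drug.

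- **SAP 9.1, exceptions after concentrations are known.** Removal from the statistical analysis "could be done after concentration data are communicated by the bioanalytical laboratory" in two cases. The first is "Any participant with lack of any measurable concentrations or only very low plasma concentrations for reference formulation", defined as an AUC below 5% of the Reference geometric mean. The second is "Any participant with non-zero baseline concentrations" above 5% of C_max, for either formulation. Low Test exposure is in neither.
- **SAP 9.2.1.** Parameters of parent and metabolite are calculated "for the participants with sufficient plasma concentration data (a PK profile with at least 3 quantifiable concentrations"). The rule does not distinguish Test from Reference, or C_max and AUC_last from parameters that need a terminal slope.
- **SAP 7.1 and Protocol 10.2.3.1.** The PK set requires in both periods "sufficient PK concentration data to support the calculation of primary PK criteria". SAP 7.1 refers to SAP 9.1 for this. The matching item there is "Any participant with insufficient PK samples to support the calculation of primary PK criteria"; it is decided case by case and sits among the rules applied before concentrations are released.
- **SAP 9.2.2.** The mixed model is fitted to ln(AVAL). Bioequivalence requires the 90% CI to lie within 0.80 to 1.25 for C_max, AUC_last and AUC_inf.

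SAP 9.1 has a separate rule that lambda_z needs at least 3 points, excluding C_max. No text says how a Test profile with fewer than 3 quantifiable values is valued or counted.

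**The concern.** The 9.1 exception is one-sided for a good reason. A failed Reference dose says nothing about the new tablet, whereas a failed Test dose is direct evidence against it. The 9.2.1 minimum cuts across this. A Test period in which every sample was drawn and assayed, but only 0 to 2 results were quantifiable, yields no C_max and no AUC_last. Either the participant leaves the comparison, or only the Test record is missing and the remaining Reference record adds little to the Test/Reference contrast. Either way the failure does not reach the interval that decides the trial.

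Such an exclusion depends on the measured outcome and favours the claim under test. The 3-value minimum is not needed to protect lambda_z, because SAP 9.1 already does that. In 9.2.1 its added effect is to withhold C_max, T_max and AUC_last as well.

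**Working it through.** **1. The plan's own figure.** Inputs from SAP 4: CV 25%, ratio 1.05, limits 0.80 to 1.25, one-sided alpha 0.05, N = 36.

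- Within-participant log-SD: s = sqrt(ln(1 + 0.25²)) = 0.246.
- SE = s × sqrt(2/N), with df = N − 2.
- Exact TOST power at N = 36 is 0.901, and 36 is the smallest even N that reaches 90%. The stated sample size reproduces.

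**2. One failed Test profile dropped.** With 35 left (18 and 17 per sequence), exact power is 0.893. The simulated median 90% CI is about 0.95 to 1.16.

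**3. The same profile kept.** Let f be the failed profile's C_max as a fraction of the expected value. One of the 36 log differences shifts by ln f, which has two effects:

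- the log point estimate moves by ln(f)/36;
- the variance of the differences becomes about 2s² + (ln f)² × (17/18)/34, with 2s² = 0.1212.

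The half-width is t(0.95; 34) × sqrt(variance/36), with t = 1.691. For f = 0.05:

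- shift = −2.996/36 = −0.083, so the ratio is 1.05 × exp(−0.083) = 0.966;
- variance = 0.1212 + 8.974 × 0.944/34 = 0.3705;
- half-width = 1.691 × sqrt(0.3705/36) = 0.172;
- 90% CI = 0.81 to 1.15.

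Pass rates below come from 60,000 simulated crossovers per case, with the sequence-adjusted t interval. That interval equals the SAP model when every participant has both periods.

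| Failed Test profile | Typical 90% CI | Chance of passing C_max |
|---|---|---|
| dropped | 0.95–1.16 | 0.89 |
| kept, f = 5% | 0.81–1.15 | 0.54 |
| kept, f = 3% | 0.79–1.15 | 0.30 |
| kept, f = 1% | 0.73–1.17 | 0.01 |

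**4. When the 3-value rule applies.** The documents give no LLOQ and no half-life figure. I applied the 17 post-dose times to a one-compartment curve, assuming a half-life of 2 to 8 h and T_max of 1 to 2 h (Protocol 3.2.5 reports 1.5 to 2 h). The third-highest sample is 91% to 98% of the profile's own peak. A smooth profile therefore falls below 3 quantifiable values only if its peak is close to or under the LLOQ.

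| Failed profile (% of usual C_max) | LLOQ (% of usual C_max) | Quantifiable values |
|---|---|---|
| 5% | 2% | 8–13 (kept) |
| 3% | 2% | 6–10 (kept) |
| 3% | 1% | 8–13 (kept) |
| 1% | 0.5% | 7–12 (kept) |
| 5%, 3% or 1% | same percentage | 1 (lost) |

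The rows in step 3 thus contrast dropping with keeping only where the LLOQ is about the same percentage of usual C_max as f. A lower LLOQ makes the lost case rarer but the contrast larger, because the lost profile then has a smaller f.

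**5. What could be calculated instead.** With 1 or 2 quantifiable values, C_max and T_max exist. The BLQ table in SAP 9.1 sets values before T_max to zero, so AUC_last can be integrated at least over the rise to the peak. With no quantifiable value, C_max is zero or missing, and ln(AVAL) has no value under any wording.

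**The case against.** A reader might infer that the plan discards any near-zero Test profile. It does not. The cut is fewer than 3 quantifiable values, not an exposure threshold, and step 4 shows that profiles at 1% to 5% of normal usually stay in if the assay reads well below them. Those keep C_max and AUC_last and count against bioequivalence, although AUC_inf may be lost under the lambda_z and 20% extrapolation rules.

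A reader might also infer that the PK-set definition in SAP 7.1 removes a low Test profile by itself. Read through its reference to SAP 9.1, it does not. The matching item concerns missing samples and is settled before concentrations are seen, so it cannot respond to a low result. What remains is a mismatch of wording: 7.1 and Protocol 10.2.3.1 speak of concentration data, 9.1 of samples.

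Three further points stand:

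- An all-BLQ profile cannot enter a log-scale model, so rewording 9.2.1 directly rescues only profiles with 1 or 2 quantifiable values.
- The event is unlikely. The tablet cores list the same excipients (Protocol 7.1), dosing is supervised with hand and mouth checks (Protocol 7.10), and the 14-participant pilot gave ratios of 0.98 to 1.05 (Protocol 3.2.5).
- Nothing would be hidden. SAP 7.2 lists exclusions with reasons, and SAP 9.2.2 lists all available profiles with excluded participants flagged.

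These points limit how often the problem arises. They do not answer it: a listing plays no part in the decision rule.

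**Conclusion.** The point holds in a narrow form. A stated rule in SAP 9.2.1, not merely a gap, takes a fully sampled Test profile with 0 to 2 quantifiable concentrations out of the bioequivalence comparison, against the Reference-only limit in SAP 9.1. The case is rare and its probability cannot be estimated from the documents. If it occurs, the chance of passing C_max is about 0.89 with the profile dropped, and 0.54 or less with it kept when the LLOQ is 5% of usual C_max or lower. These figures rest on the SAP 4 assumptions, exactly one failure among 36, and a kept C_max near the LLOQ. The documents do not support a general claim that failed Test doses are dropped.

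The change is worth making because one participant can reverse the conclusion and the correction is only wording. The choice would be hard to defend if made after such a profile had been seen in an open-label trial.

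**What to change.** 1. **SAP 9.2.1:** apply the 3-value minimum only to lambda_z-dependent parameters. Calculate C_max, T_max and, where at least one interval can be integrated, AUC_last for every fully sampled profile with at least 1 quantifiable post-dose value.
2. **SAP 7.1 and Protocol 10.2.3.1:** align the sufficiency wording with the missing-samples wording of SAP 9.1, and state that low or BLQ results after a Test dose are not a reason to leave the PK set.
3. **SAP 9.2.2:** if a fully sampled Test profile is entirely BLQ, report it beside the primary 90% CI, with a pre-specified sensitivity analysis that sets Test C_max to the LLOQ.

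The cost is a few sentences in the SAP and one clause in the protocol. No sample, visit or dose changes. The downside for the sponsor is that a true Test failure would count against bioequivalence.
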